# 5.8 Data Collection

Self-reported responses from surveys will be collected from participants after 8 weeks of use for each device via e-mail (REDCap Survey) or mailed paper surveys. If a participant does not have access to email then the survey will be mailed for completion with a self-addressed envelope with pre-paid postage. Data from the medical record will be abstracted for all participants that are registered in the study to capture demographics, socio-economic status, utilization, standards of prenatal care, delivery outcomes and safety data. The time frame for collection will be from time of enrollment to the 6-8 week postpartum appointment.

Gestational Weeks	12 wks	18-20	24 wks	28 wks	32	36 - 37
		wks			wks	wks
Subject interest	Х	Х				
Subject eligibility	Х	Х				
Informed consent		Х				
Fetal Anatomy Sonography		Х				
Independent Device Use		Х		Х		
Assessment						
Weekly device use		Х	Х	Х	Х	Х
SUS Survey				Х		X

Table 2: Outline of data	collection	by weeks o	f pregnancy.

## **5.9.1 Participants Demographics**

Participant characteristics to be collected at time of enrollment through self-report and medical record review will include: age, race/ethnicity, education level, marital status, BMI, due date, parity, previous miscarriage, previous C-section and insurance.

## 5.9.2 Participants Reported Outcomes

System Usability Survey: Ease of use will be evaluated using a survey assessing comfort with use, troubleshooting, ease of obtaining FHR, any safety concerns, and whether or not the device was useful for confirming fetal well-being.

Medical device usage: While mothers are using the standard home Doppler they will be asked to track usage information. These metrics will include date of use, user (mother/partner), estimated time to find FHR, and estimated FHR.

## 5.9.3 Clinical/Practice Important Outcomes

Safety and Healthcare Utilization: Data will be captured from the medical record review and participant's report of any safety concerns. A medical record review will be conducted to capture

all in-office visits within the OB Clinic, all triage visits and any hospitalizations that were prompted by FHR monitoring obtained at home, and recorded on the study case report form.

Patient engagement with remote monitoring devices will be measured by the number of times patients record FHR or both MHR and FHR data. Participant compliance with instructions regarding frequency of device use will be assessed by reviewing the device use statistics gained from information automatically uploaded to the HIPAA compliant cloud storage each time the device is used (*Appendix B* and https://hera-med.rmdy.health/CoachConsole/Account/Login).

Participants who use the device more often than what is recommended will be re-instructed on appropriate use (once weekly).

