  - b. Hypothesis: The intervention will reduce the rate of healthcare utilization without impacting maternal safety or the process of care standards specified by the American College of Obstetricians and Gynecologists (ACOG).

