# 5.0 Study Methods

# 5.1 Overview

Primary Objective

- 1) To evaluate the functionality of HeraBEAT™ when self-administered by pregnant women by assessing the following:
  - a) Study participants' independent use of the device assessed by study personnel observation, including ability of participants to read and follow HeraBEATTM device instructions, and find fetal heart rate without assistance evaluated using the HeraBEATTM Independent Device Assessment Form. (*Appendix C*).
  - b) Data transmission from the device to the healthcare provider via a HIPAA compliant cloud-based server, assessed by evaluating the data transmitted to the healthcare provider from the HeraBEAT™ US device, including subject' success in finding FHR, time to find FHR, frequency of use, and clinical utility of the FHR/MHR data (*Appendix B*).

Secondary Objective

- 1) To evaluate the acceptability of HeraBEAT™ when self-administered by a pregnant women in the home by assessing the following:
  - a) Patient usability and ease of use assessment as measured by the System Usability Scale (SUS), *Appendix D*.
  - b) Impact on utilization of care as measured by urgent triage and/or emergency care visits for concerns regarding fetal well-being.

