## **5.7 Intervention**

All randomized participants will be assigned to an obstetric physician, midwife or combination of physician/nurse practitioner care team that will supervise care during her pregnancy. All laboratory tests, imaging, and standardized evaluations that ensure the safety of the participant and her fetus will be conducted in both arms of the study as per departmental protocol.

Participants will be instructed to seek care (per routine obstetric precautions) for any concerns regarding fetal wellbeing, irrespective of their FHR on home monitoring devices. No clinical decisions will be solely based on the results of home monitoring data. Data uploaded from the HeraBEATTM device will be monitored by trained study personnel via the HeraBEAT dashboard : https://hera-med.rmdy.health/CoachConsole/Account/Login. FHR abnormalities will be investigated, using standard obstetric clinical protocols.

All adverse events (AEs) experienced by the subjects while at home or in the clinic will be recorded on the HeraBEATTM study case report form and evaluated for type of event, severity, whether the AE qualifies as a serious adverse event (SAE), and relationship of the AE to the HeraBEATTM device use.

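### The utilization capture rule in section 5.9.3 does not match secondary objective 1b: it omits emergency care, adds a home-FHR qualifier, and names no reason for visit

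*Combined protocol and SAP*

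**What the plan says.** - **Hypothesis.** Section 1.0, hypothesis 2b, gives a direction: "The intervention will reduce the rate of healthcare utilization".
- **Endpoint.** Section 5.1, secondary objective 1b, reads: "Impact on utilization of care as measured by urgent triage and/or emergency care visits for concerns regarding fetal well-being". It does not require that a home reading led to the visit.
- **Capture rule.** Section 5.9.3 says that record review will capture all OB clinic visits, and then "all triage visits and any hospitalizations that were prompted by FHR monitoring obtained at home", with entry on the study case report form.
- **General abstraction.** Section 5.8 says: "Data from the medical record will be abstracted for all participants that are registered in the study to capture demographics, socio-economic status, utilization", among other items. It adds: "The time frame for collection will be from time of enrollment to the 6-8 week postpartum appointment". There is no home-FHR limit here, but also no list of visit types or reasons.
- **Care seeking.** Section 5.7 tells participants to seek care "for any concerns regarding fetal wellbeing, irrespective of their FHR on home monitoring devices".
- **Comparator.** Under sections 5.5 and 5.6 every woman uses a home device in both periods: HeraBEAT in one and a standard Doppler in the other, switching at about 28 weeks.
- **Analysis.** Section 8.0 has no analysis specific to utilization. It has only a general ad-hoc rule of t-tests and chi-square tests between study arms.

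**The concern.** An endpoint needs a capture rule that collects the events it counts. Here the rule and the endpoint differ in event type, in the condition placed on the event, and in whether the reason for the visit is recorded. Two abstractors could follow the same sentence in 5.9.3 and build different datasets.

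The condition matters most for hypothesis 2b. A device that reassures a woman could spare her a visit that no home reading would have prompted, for example one for reduced movement. Section 5.7 makes clear that such visits are expected. If they are not recorded, a fall in them cannot be seen. Whether a visit was prompted by a home reading is also an attribution, and participants and study clinicians know which device is in use (section 8.0).

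**Working it through.** The documents state no utilization rate, effect size or power, so there is no figure to reproduce. The check is a comparison of the text, followed by an illustration on stated assumptions.

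**Step 1: set the endpoint beside the capture rule.**

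| Element | Objective 1b (5.1) | Capture rule (5.9.3) |
|---|---|---|
| Triage visits | Counted if urgent and for a fetal concern | Listed |
| Emergency visits | Counted if for a fetal concern | Not listed |
| Clinic visits, hospitalizations | Not part of the measure | Listed |
| Condition | Concern about the fetus | Prompted by home FHR (scope unclear) |
| Reason for visit | Needed to classify the event | No item named |

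**Step 2: the two readings of 5.9.3.**

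- *Reading (a):* the qualifier limits hospitalizations only. All clinic and triage visits are captured. Emergency visits remain unlisted, and triage visits cannot be classified without a reason.
- *Reading (b):* the qualifier limits all three event types. Fetal-concern triage visits that no home reading prompted are lost as well.

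**Step 3: what reading (b) would do to the comparison.** All inputs are assumptions except the number of women. Section 8.2 plans 50 participants with up to 10% loss: 50 × (1 − 0.10) = 45. Let b be the number of fetal-concern visits per woman per period (0.2 to 0.4), f the share prompted by home FHR (0.10 to 0.50), and r = 0.30 the relative reduction on HeraBEAT.

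- If only non-prompted visits fall, the objective's rate ratio is (1 − f)(1 − r) + f = 1 − 0.30(1 − f). The prompted count does not change, so reading (b) gives 1.00.
- If only prompted visits fall, the objective's rate ratio is 1 − 0.30f, and reading (b) gives 1 − 0.30 = 0.70.

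| f | Non-prompted fall: objective | Non-prompted fall: reading (b) | Prompted fall: objective | Prompted fall: reading (b) |
|---|---|---|---|---|
| 0.10 | 0.73 | 1.00 | 0.97 | 0.70 |
| 0.25 | 0.775 | 1.00 | 0.925 | 0.70 |
| 0.50 | 0.85 | 1.00 | 0.85 | 0.70 |

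Expected comparator-period counts for the objective run from 45 × 0.2 = 9 to 45 × 0.4 = 18. Under reading (b) they run from 45 × 0.2 × 0.10 = 0.9 to 45 × 0.4 × 0.50 = 9. Reading (b) therefore hides one kind of reduction and exaggerates the other relative to the objective, on few events.

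**Step 4: does section 5.8 close the gap?** In part. It allows abstraction of utilization without the home-FHR limit, but names no emergency visits, reason for visit or device period. Its window runs to the postpartum appointment, whereas devices are used from 20 to 36/37 weeks (section 5.6). Visit dates are therefore needed to place an event in a device period. The documentation of calls in section 5.5 covers telephone contacts, not visits.

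**The case against.** The strongest reply is that section 5.8 already provides for utilization to be abstracted for every registered participant, and that reading (a) is the natural one because the wording of 5.9.3 moves from all to any before the qualifier. On that view every triage visit is collected and only emergency visits are unlisted. If obstetric emergencies at this center come through triage, little would be lost; the documents do not give the split. The case report form is not in the supplied text and may hold the missing fields.

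Much of this stands. A reader might infer that the endpoint cannot be computed at all, and section 5.8 does not support that. A reader might also infer that the plan could never show a reduction. That would require a comparator without home monitoring, whereas both periods have it, so fewer prompted visits on HeraBEAT would show even under reading (b).

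What does not stand is that 5.8 settles the matter. Its provision is a single undefined term, 5.9.3 is the section that spells it out, and the two sections differ. It is also fair to say that classifying a visit as a fetal concern takes judgement too. Using the reason recorded at the visit limits that judgement but does not remove it.

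**Conclusion.** The concern holds as a conflict between a stated endpoint and its stated capture rule. Under either reading of 5.9.3, emergency visits are not listed and no reason for visit is named. Under the restrictive reading, fetal-concern visits not prompted by a home reading are also missed, and a reduction in them would not show. With the assumptions above, a true rate ratio of 0.73 to 0.85 would then appear as 1.00.

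That range is an illustration, not an estimate. It rests on an assumed prompted share, an assumed 30% effect confined to non-prompted visits, and reading (b). A reader might want to state what fraction of endpoint events would be lost. The documents give nothing to anchor it, since any such figure is one minus an assumed share.

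The point concerns a secondary objective. It does not touch the SUS comparison that section 8.2 names as the primary outcome, and no power is claimed for utilization. It should be corrected because it bears directly on hypothesis 2b, and reasons and dates may be hard to recover consistently if they are not collected as the trial runs.

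**What to change.** Amend section 5.9.3, and refer to it from section 5.8, as follows.

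1. Abstract all triage, emergency and unscheduled OB visits and all hospitalizations during the device periods (20 to 36/37 weeks), each with its date and the reason recorded at the visit.
2. Define the objective 1b endpoint as triage or emergency visits for fetal well-being concerns, whatever prompted them.
3. Record whether the visit was prompted by home FHR as a separate yes/no flag. It should describe the event and not decide whether it is counted.
4. Attribute each visit to the device assigned for that period under the randomized sequence, in line with the intention-to-treat rule in section 8.0.
5. In section 8.0, name a between-device comparison within woman. Each arm uses both devices, so totals by arm over the whole study would compare sequences and not devices.
6. Check that the case report form carries these fields.

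The cost is slightly more record abstraction, from records already under review, with no added burden on participants.

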#### 6.0 Follow-up Guidelines

All participants will be followed per protocol guidelines and deviations from protocol will be reported to the IRB. If a participant refuses to continue to participate and consent is withdrawn, they will then be considered a withdrawn participant and no further data will be collected through medical review or self-report. Participants withdrawn prior to the end of the study will turn in their device at the time of withdrawal and continue routine prenatal care.

## 7.0 Stop Guidelines

All enrolled participants may choose to discontinue at any time. Since they will already be assigned to an obstetric provider, no interruption of care will be introduced. Participants may also be asked to discontinue the study if their pregnancy is subsequently diagnosed as high risk, or if cardiac or cranial anomalies are identified on routine fetal sonography.

#### 8.0 Data Analysis Plan

The study will be analyzed according to the intention to treat principle, including all mothers randomized to the study in the arm to which they were randomized, regardless of whether they received the intervention assigned.

Baseline characteristics will be reported in the study results with continuous values being reported as means and standard deviations or median interquartile range as appropriate. Categorical values will be reported as counts and proportion. Two sample t-tests or Wilcoxonrank sum test and chi-squared tests or Fishers exact test will be used as appropriate. Any baseline imbalances (p<0.05) will be explored as a possible confounder to adjust for when the outcome measures are analyzed. We will adhere to the CONSORT guidelines to transparently

report study results and ensure that sufficient information is included to allow for assessment of the study's internal and external validity.

Ease of use will be estimated from the System Usability (SUS) validated questionnaire. These data will be analyzed as a two sample t-test prior to cross over. After cross over we will analyze these data using an ANCOVA adjusting for order of medical devices or as a paired t-test as appropriate.

Within the SUS survey, we will also examine trends within individual questions using chi-square tests. Clinical concerns in FHR will be indicated as a FHR less than 110 bpm or greater than 160 bpm. These data will be analyzed as McNemar's test on the association of the study medical devices with the clinical standard of care. Comparing ease of use metrics will be done using an ANCOVA analysis or generalized estimating equation as appropriate adjusting for gestational age. Additional ad-hoc analysis will be performed using standard techniques appropriate for randomized trials, with each outcome compared between study arms using t-tests for continuous outcomes and chi-square tests for dichotomous outcomes. If there are differences in baseline characteristics between the two study groups, these will be accounted for using ANCOVA or regression models which include an indicator for study arm.

Participants and study clinicians (nurses, obstetric providers) will not be blinded to the intervention after randomization occurs. Study statistician and data analysts will be blinded as to which arm participants were assigned to. Statistical analysis performed by Mayo Clinic Statistician and [name], MSc, Statistical Consultant, Rabin Medical Center, Beilinson Hospital, Israel.

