## 5.5 Study Design

As part of current standard of care, pregnant women are initially evaluated by an obstetric physician, nurse practitioner or midwife during the first trimester. During this visit, the study nurse will complete the assessment for eligibility criteria for low risk pregnant women. Upon confirmation of eligibility, the nurse will contact the study coordinator. The study coordinator will approach the patients with study information, ascertain interest in participation, and obtain signed informed consent from those interested.

Between 18 and 20 weeks gestation, all patients complete a fetal sonography assessment for fetal anatomy as part of routine prenatal care. An obstetric provider will review the results with the patient, and confirm that fetal anatomy is normal. Patients with abnormal fetal cardiac or cranial anomalies will be excluded from the study. If the patient interest remains, the study coordinator will confirm ongoing consent and randomize the patient into the study. This will be documented in the appropriate section of the patient's electronic medical records.

Study personnel (obstetric nurses or clinicians) will then provide patients with a study kit, containing the HeraBEATTM device or a standard fetal Doppler device (based on randomization assignment), discuss the limitations of both devices, and instruct patients on the range of normal fetal heart rate.

Study personnel will then observe the study subjects' independent self-administration of the devices in the prenatal clinic after patients receive a brief tutorial of the devices operation. Study subjects will be able to refer to the device instructions for use but will not receive assistance or prompts during this testing session. Study personnel will note any mistakes or difficulties by the subjects on the HeraBEATTM Independent Device Use Assessment Form (Appendix C). Once the observation period is completed, study personnel will document all observations, review and correct any errors made by patients during use of the device, assist patients in confirming accurate use, perform teach back, and provide the study subject with a device for home use. Patients will be instructed to call clinic or Triage with any questions or concerns regarding results of fetal monitoring at home. All calls and recommendations provided will be documented.

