## 5.6 Schema

Patients will be instructed to monitor their fetus once weekly, using their assigned device, from 20 weeks to 36/37 weeks gestation. Patients using the HeraBEATTM device will have their FHR and MHR data displayed on their App, and uploaded to a HIPPA compliant cloud based server, which can be accessed by the healthcare provider for review (*Appendix B*). Patients using the standard handheld Doppler device will be given a study brochure for recording their weekly data. Patients using the HeraBEATTM device will be instructed to bring their device during their outpatient clinical appointments, for comparison of MHR and FHR during their routine clinic appointments using methods documented in *Appendix E*.

After approximately 8 weeks of monitoring, patients will complete a System Usability Survey (SUS Survey), *Appendix D* to assess ease of use of the device, then crossover to the alternate study product.

Patients who are randomized to HeraBEATTM from 20weeks gestation to 28 weeks gestation will be given the standard fetal Doppler. Patients who are randomized to the standard Fetal Doppler will switch to the HeraBEAT.TM At the conclusion of each patient device use (28 weeks and 36 weeks gestation), participants will complete the System Usability Survey (Appendix D) to assess ease of use of each device.

- 1- Nurse assesses eligibility criteria, ascertains mother's interest, and study coordinator will obtain consent and complete randomization Patients will be given home monitoring equipment after their fetal anatomy sonography is complete, inclusion/exclusion criteria confirmed and Patient Usability Form completed (Appendix C).
- 2- After 8 weeks of use, participants will complete the System Usability Scale (SUS) survey (Appendix D), return the first study device and crossover to the second device. An independent device use assessment (Appendix C) will be assessed by study nursing staff and completed for the second device.
- 3- At the conclusion of 8 weeks of self-monitoring with assigned device, participants will complete the System Usability Scale (SUS) survey to assess ease of use (Appendix D).

Prior to registering study participants, all eligibility criteria will have been met and fully documented. Mothers will be randomized by the study coordinator after completion of standard informed consent for participation in clinical research including permission to use Protected Health information.

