## 8.2 Sample Size

Difference in ease of use between our standard fetal Doppler and HeraBEAT™ device, as measured by the System Usability Survey (SUS) will be the primary outcome. Approximately 1500 – 2000 expectant mothers receive prenatal care in the obstetric department annually. We aim to recruit 50 participants (50 per arm, with cross-over) for a 99.7% power to detect a 10-point difference in SUS, as this accounts for a withdraw / post-randomization exclusion, estimated as high as 10% (assuming a proportion of expectant mothers to withdraw participation after being enrolled or found to not meet criteria after the fact).

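### After crossover, SUS may be tested with no period term and SUS items with no pairing: specify one period-adjusted analysis, and settle whether SUS is primary

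*Combined protocol and SAP*

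**What the plan says.** **Status of SUS.** Section 8.2 says that the difference in ease of use "as measured by the System Usability Survey (SUS) will be the primary outcome". Section 5.1 places the same measure under the Secondary Objective: "Patient usability and ease of use assessment as measured by the System Usability Scale (SUS"). The Primary Objective there is functionality and does not mention SUS.

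**Timing.** Section 5.6: "At the conclusion of each patient device use (28 weeks and 36 weeks gestation), participants will complete the System Usability Survey". Before home use of a device, staff observe the woman using it and then, in section 5.5, "review and correct any errors made by patients during use of the device, assist patients in confirming accurate use, perform teach back". Section 5.6 repeats the observed assessment for the second device.

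**Analysis.** Section 8.0 gives a two-sample t-test for the scores before crossover. After it: "After cross over we will analyze these data using an ANCOVA adjusting for order of medical devices or as a paired t-test as appropriate". Individual SUS questions are to be examined with chi-square tests; McNemar's test is named only for fetal heart rate concerns. A further sentence reads: "Comparing ease of use metrics will be done using an ANCOVA analysis or generalized estimating equation as appropriate adjusting for gestational age". It does not say whether these metrics include the SUS total.

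**Size.** Section 8.2 plans "50 participants (50 per arm, with cross-over) for a 99.7% power to detect a 10-point difference in SUS", allowing for "withdraw / post-randomization exclusion, estimated as high as 10" percent. It gives no SD, within-woman correlation, alpha or test.

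**The concern.** Every woman's second survey comes 8 weeks later in pregnancy than her first, after more home monitoring and a second round of observed use. A shift in SUS between periods, whatever the device, is therefore plausible. The plan's own wish to adjust ease-of-use metrics for gestational age points the same way, since gestational age and period move together here.

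A paired t-test pools the within-woman differences of both sequences as one sample. A period effect pushes the two sequences in opposite directions. That inflates the variance and, if the sequences differ in size, shifts the mean. The alternative on offer, an ANCOVA for order, removes period if it is fitted to within-woman differences. It does not if order is a between-woman covariate on stacked scores. The text does not say which is meant, so the method could be chosen after the scores are seen, on the outcome that sizes the trial.

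Two related points. If chi-square tests compare devices item by item over both periods, they treat two ratings by one woman as independent. And while sections 5.1 and 8.2 disagree, a reader cannot tell which result decides the trial.

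**Working it through.** From the documents: 50 women, 10-point target, loss of up to 10% (50 × 0.9 = 45 completers), surveys at 28 and 36 weeks. Everything else (SDs, correlations, period effects, splits, two-sided 5%) is assumed.

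**1. The plan's 99.7%.** It can be neither confirmed nor refuted. Several input sets give it for 10 points by the noncentral t:

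| Test | SD needed |
|---|---|
| Period-adjusted, 25/25 | 14.7 (within-woman difference) |
| Period-adjusted, 23/22 | 13.9 (within-woman difference) |
| Independent groups, 50 v 50 | 10.5 |
| Independent groups, 45 v 45 | 10.0 |
| First period only, 25 v 25 | 7.4 |

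**2. The two estimators.** Let D be HeraBEAT minus Doppler within a woman, d the true difference, π the period effect (second minus first) and σ the SD of D. The n1 women who start with HeraBEAT have mean d − π; the n2 who start with Doppler have mean d + π.

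- Paired t-test: expectation d + π(n2 − n1)/N. At n1 = n2 the expected sample variance is σ² + π²N/(N − 1).
- Period-adjusted (mean of the two sequence means): expectation d, SE = (σ/2)√(1/n1 + 1/n2), N − 2 degrees of freedom.

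At 25/25 and σ = 15:
- Adjusted SE = 7.5 × √(2/25) = 2.12.
- Paired SE at π = 5: √[(225 + 25 × 50/49)/50] = 2.24.
- Paired SE at π = 10: √[(225 + 100 × 50/49)/50] = 2.56.

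Simulation at 25/25, σ = 15:

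| π | Paired size | Paired 95% CI width (adjusted 8.49) | Paired power, d = 5 (adjusted 64%) | Paired power, d = 10 (adjusted 99.6%) |
|---|---|---|---|---|
| 0 | 5.0% | 8.48 | 64% | 99.6% |
| 5 | 3.8 to 3.9% | 8.95 | about 60% | 99.5% |
| 10 | 1.9% | 10.23 | 48% | 98.7% |

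The adjusted size is about 5% throughout. Width ratios are 8.95/8.49 = 1.05 and 10.23/8.49 = 1.21.

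**3. Other SDs** (π = 10, d = 5, 25/25):

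| σ | Paired power | Adjusted power | Paired size |
|---|---|---|---|
| 10 | 75% | 93% | 0.6% |
| 15 | 48% | 64% | 1.9% |
| 20 | 32% | 41% | 2.8% |
| 25 | 24% | 28% | 3.5% |

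**4. Unequal sequences.** From 25/25 with all five losses in one sequence (25/20), the bias is 5/45 of π: 0.56 points at π = 5 and 1.11 at π = 10. Its sign depends on which sequence loses women. At σ = 15 the size is 4.6% and 3.4%, so there is no inflation. That depends on a 25/25 start, and the plan states neither an allocation ratio nor blocking. At 27/18 and π = 10 the bias is 9/45 × 10 = 2.0 points and the size about 7% to 8% (σ from 12.5 to 17.5).

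**5. Cost of adjusting when π = 0** (d = 5, σ = 15): none at 25/25 (63.7% either way); 58.3% v 58.9% at 25/20.

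**6. SUS items** (45 pairs, five categories at 5/10/20/35/30%, 65% agreeing, no period effect, latent within-woman correlation 0.3, 0.5, 0.7). Chi-square on agree v not agree has size 3.0%, 2.0% and 0.6%; McNemar mid-p has 4.6%, 4.6% and 4.1%. Power for 81% v 65% is 42%, 41% and 41% for chi-square against 46%, 52% and 61% for McNemar. Comparing within-woman item differences between sequences, on the five-point score, holds size near 5% with power from 67% to 94%. Part of that gain comes from not dichotomising.

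**7. What period adjustment does not cure.** Device-specific carry-over biases the crossover estimate by half its size. At 23/22, SD 15 and correlation 0.5, carry-over of 2 or 4 points gives 1.0 or 2.0 points of bias and size 7.2% or 14.1%. The first-period t-test stays at 5.0%, but its power at 10 points with 23 v 22 is only 90.6%, 74.6% and 58.9% at SD 10, 12.5 and 15.

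**8. Power of the recommended test**, 23/22, 10 points:
- σ = 15: SE = 7.5 × √(1/23 + 1/22) = 2.24, noncentrality 10/2.24 = 4.47, power 99.2%.
- σ = 20: 90.6%.
- σ = 25: 74.6%.

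**The case against.** The adjusted analysis is already the first option named in section 8.0, and a gestational-age ANCOVA or GEE would largely act as a period term. What is wrong is an unresolved choice, not a missing method. That is fair, and it sets the weight of the point, but the choice stays open and the form of the ANCOVA is not given.

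The harm is small where the trial is sized: at 10 points the paired test has 98.7% power or more in the 25/25, SD 15 cases. The larger losses need both a smaller true difference and a period effect as large as the planned device effect, and nothing in the documents supports that size. With period effects of 2 or 3 points the interval is only 0.9% or 2% wider, and power at 5 points is 63.3% or 62.3% against about 64%. This stands. So does the remark that the first survey also follows training and 8 weeks of use; only the added experience and later gestation separate the two.

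The item point is inferred. The plan does not say that both periods are used, a first-period chi-square test would be valid, and the error is conservative in an exploratory analysis. This also stands, and the point is conditional on it.

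Making the first-period t-test supportive gives up protection from carry-over. True, but the paired t-test shares that bias, and keeping the first-period result beside the crossover estimate preserves the check.

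**Conclusion.** The concern holds, as a change that should be made. The conflict between sections 5.1 and 8.2 over the status of SUS is wrong as written and needs no assumptions. The permitted paired t-test is inferior to a period-adjusted analysis whenever a period effect exists, and costs at most a fraction of a percentage point of power to replace when none does. Its consequence is mainly wasted precision: intervals 5% to 21% wider for assumed period effects of 5 to 10 points at a within-woman SD of 15, with negligible loss at the planned difference. Bias needs unequal sequences as well as a period effect; inflated type I error needs a marked imbalance such as 27/18. The chi-square criticism applies only if items are compared over both periods. The 99.7% power is not shown to be wrong; it cannot be checked.

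**What to change.** - **8.0, SUS total.** Name one main analysis: device, period and sequence as fixed effects and woman as random effect, or equivalently the period-adjusted comparison of within-woman differences between sequences. Report HeraBEAT minus Doppler with a 95% CI at two-sided 5%. Delete the paired t-test option.
- **8.0, supporting analyses.** Keep the first-period t-test as the check free of carry-over, and state that device-specific carry-over biases the crossover estimate by half its size. If the gestational-age ANCOVA or GEE covers the SUS total, label it a sensitivity analysis.
- **8.0, SUS items.** Compare devices with a paired method that also carries period, for example within-woman item differences compared between sequences.
- **5.1 and 8.2.** Give SUS one status, and check that the aims in section 1.0 agree.
- **8.2.** State 50 women, about 25 per sequence and about 45 completers, with the assumed SD of the within-woman difference, alpha, test and resulting power.

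The cost is wording: no extra women, visits or data, and one degree of freedom for period. The stated power may fall below 99.7%, and preferring the crossover model accepts the carry-over risk described above.
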